At NU, the trial will be primarily implemented at the Robert H. Lurie Comprehensive Cancer Center. [name] is Director of the cancer center and will ensure that this trial is integrated into the cancer center clinics to facilitate recruitment. Cancer Center data indicate that ~6000 new patients/year are seen at the NU cancer center. Preliminary data ascertained for this proposal showed that, among 127 eligible cancer patients screened, 17 were smokers (13%) and 12 (71%) agreed to enroll in a smoking cessation program. Thus, based on ~6000 patients available for screening/year, we expect that ~780 will be smokers and ~546 will be interested in this study. Given the trial requirements and inclusion/exclusion criteria, we estimate that we can enroll ~10% of these patients for this trial (Martinez et al., 2009) or ~55 patients/year at NU (total sample at NU = 187 over 4 years).

Both PENN and NU will supplement recruitment with referrals from physicians and other cancer care providers at various cancer treatment centers within the Philadelphia and Chicago metropolitan areas.

Based on our extended therapy and bupropion trial with cancer patients ([name] et al., 2010a, 2010b), we expect that <20% of participants will withdraw from the trial and ~70% of participants will complete follow-up evaluations, which will exceed rates in varenicline trials (Jorenby et al., 2006). As is advised in smoking cessation trials (Hughes et al., 2003), intent-to-treat will be used for primary analyses, with missing outcome data coded as smokers (even due to death).

3. Key Inclusion Criteria

Eligible subjects will be males and females:

1. 18 years of age or older who self-report smoking at least 5 cigarettes per week, almost every week (menthol and non-menthol) on average, for the last 6 months.
2. Who have been diagnosed with a primary or secondary cancer (all sites) or have experienced a recurrence of a previously diagnosed cancer within the past 5 years. Those diagnosed >5 years ago without remission will also be eligible.
3. With a Karnofsky Score of ≥ 50 or ECOG Performance Status score of ≤ 2 within 6 months of enrollment.
4. Able to use varenicline safely, based on a medical evaluation including medical history and physical examination, and psychiatric evaluation.
5. Residing in the geographic area for at least 12 months.

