Smoking status is assessed using the timeline follow-back method (Brown et al., 1998) as done previously (Lerman et al., 2004; [name] et al., 2010b) and by using breath CO to verify self-report. Participants are considered abstinent if they self-report abstinence (not even a puff of a cigarette) for >7 days prior to the Week 24 and 52 assessment and have a breath CO of <10ppm at the time-point (SRNT, 2002; Hughes et al., 2003). As per convention, participants are assumed to be smoking if they self-report to be smoking at the time-point, cannot be reached to provide data at the time-point, fail to provide a breath sample at the time-point, or provide a breath sample at the time-point that is >10ppm (SRNT, 2002).

Cessation/Smoking Rate: Daily smoking (presence and rate) will be assessed at each visit after Intake Session with the well validated timeline followback method (TLFB). These data can be used to assess

the timing and rates of lapses (smoking episodes not lasting 7 days), recovery events (return to abstinence), and relapse events, as well as to monitor changes in smoking rates (i.e., # cigarettes/day). These data will also be used to compute and assess secondary measures of smoking cessation (e.g., continuous and prolonged abstinence).

Carbon Monoxide (CO) Test: Carbon monoxide will be measured at each in-person visit to confirm smoking status.

Other Smoking Measures (secondary)

As per recommendations (Hughes et al., 2003), we will also assess: prolonged abstinence to Weeks 12, 24, and 52 (relapse is 7 consecutive days of self-reported smoking, after a 2-week grace period), continuous abstinence at Weeks 12, 24, and 52 (no smoking between the quit day and follow-up), time to 7-day relapse (no grace period), smoking rate, and lapse (smoking episodes < 7 days) and recovery (return to 24-hour abstinence) events.

Quality of Life (QOL)

The Short-Form Health Survey (SF-12) will assess QOL (Ware et al., 1996). This scale yields physical and mental subscales, has been used to assess cancer patient QOL (McCorkle et al., 2009), has demonstrated validity and reliability (Gandek et al., 1998), and has been used in smoking cessation trials with cancer patients ([name] et al., 2010a). The SF-12 will be administered at all visits following the Intake Session.

2. Statistical Analysis

Power

Power is provided for the primary aims since the exploratory aim is hypothesis generating. All comparisons are 2-sided.

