Aim 1: The primary analysis is a comparison in Week 24 and Week 52 point prevalence quit rates between standard and extended therapy. For the week 24 comparison, we based our sample size on the expectation that the quit rate in the standard arm would be equal to the Week 24 quit rates reported in past clinical trials of varenicline for participants who received 12 weeks of treatment (i.e., 33%; Gonzales et al., 2006). We also expect to see at least the same effect on week 24 quit rates here as we saw in our past extended treatment trial (i.e., an OR of 1.81 or a difference of ~14%; [name] et al., 2010b). Thus, we have 80% power (alpha .05) with a sample of 374 if the difference between treatment arms in Week 24 quit rates is 14% (i.e., Week 24 quit rates for extended therapy is 47%). For the Week 52 comparison, we can expect a Week 52 quit rate for the extended arm of 56% (Tonstad et al., 2006), vs. 28% for standard treatment (Gonzales et al., 2006), for which we have 99% power (alpha = .05) with n = 374; we are powered to detect a difference at Week 52 of 14% if the present study yields a smaller effect than expected based on past studies.

Aim 2: The primary analysis is a comparison in Week 24 and Week 52 differences in QOL and severe side effects. For QOL, we have 80% power to detect a mean difference of 0.87 in physical QOL and a mean difference of 1.2 in mental QOL at any time-point, effects seen previously ([name] et al., 2010a). For side effects, the analyses will involve a test of non-inferiority since we cannot use standard statistical tests and conclude that a non-significant comparison means that the treatments are equal (i.e., “the absence of evidence is not evidence of absence”). In our past bupropion study ([name] et al., 2010a), 95% of placebo and 88% of bupropion participants reported no severe side effects. Assuming a similar difference, we have 90% power to detect equivalence with a floor of 80%, or an extended group that is 15% < the standard group.

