Aim 1: Compare standard varenicline treatment (12-weeks active then 12-weeks placebo) to extended varenicline treatment (24-weeks active) for treating nicotine dependence among cancer patients. The hypothesized effect of treatment arm (i.e., the difference in quit rates between subjects receiving standard or extended treatment) will be tested by a treatment arm term in a binomial family with logit link (logistic regression) model that possibly includes terms for covariates. Outcomes of the logistic regression analyses will be characterized by odds ratios (e.g., odds of quitting smoking) and 95% confidence intervals. Although quit-rates at the end of 24 and 52 weeks will represent our primary outcome variables, similar logistic regression analyses will be performed for other assessments of quit rates (e.g., quit rates at Weeks 12 and 26). This model will be used for measures of prolonged and continuous abstinence as well. In addition, as many participants will fail to become completely abstinent, the negative binomial family log link for count data will be used to examine the main effects of treatment arm on changes in smoking rate. Time to (recurrent) event models will be fitted using Cox regression, stratified by event sequence, as in [name] et al. (2010).

Aim 2: Assess effects of extended varenicline therapy on QOL and varenicline side effects. Repeated-measures MANOVA will examine differences across treatment arms in mental and physical QOL over the trial. Covariates will be included, such as medical treatment history. We will compare treatment arms in terms of the frequency of severe side effects (individual and total). Logistic regression will test against the lower boundary on percent reporting only mild-moderate (i.e., < severe) side effects. The hypothesis test for equivalence is whether the OR is out of the prescribed range for the difference between the treatment arms.

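### The smoking-rate analysis fits one negative binomial to data expected to hold 28–56% exact zeros and names no robust variance; its default error bars are likely to be wrong, and its rate ratio includes quitting

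*Combined protocol and SAP*

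**What the plan says.** Under 2. Statistical Analysis, Data Analysis, Aim 1, after the logistic models for abstinence, the plan adds that "the negative binomial family log link for count data will be used to examine the main effects of treatment arm" on changes in smoking rate. The reason given is that "as many participants will fail to become completely abstinent". It does not state how dispersion is set, which variance estimator is used, which time-point is analysed, whether baseline rate is a covariate, or whether abstainers are in the model.

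Other sections bear on this:
- Outcomes Variables describes timeline follow-back data used to "monitor changes in smoking rates (i.e., # cigarettes/day"). It defines abstinence as no smoking at all over the 7 days before the visit, so a confirmed abstainer has a count of zero.
- Power, Aim 1 takes a Week 24 standard-arm rate of 33% and says "Week 24 quit rates for extended therapy is 47"%. For Week 52 it expects 28% (standard) and 56% (extended).
- Accrual expects that about "70% of participants will complete follow-up evaluations". It codes missing abstinence data as smoking but gives no cigarette count for those participants.
- Data Analysis makes intent-to-treat the primary method for the study aims and adds a completers-only analysis.

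**The concern.** The expected data are a block of people at exactly zero and a spread of continuing smokers above zero. A negative binomial has one dispersion parameter for both. Maximum likelihood raises it to accommodate the zeros, and the model then overstates the variance of the arm effect. If software instead holds dispersion at 1, a common setting for a negative binomial family in a generalised linear model, the variance can be understated. Which error occurs depends on a setting that the plan does not state.

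The ratio also needs a clear label. The stated motive is the participants who do not become abstinent, yet with abstainers included a difference in quit rates alone lowers the ratio. A real effect on consumption could be missed, or a significant ratio could be read as reduction among non-quitters when it repeats the abstinence result.

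**Working it through.** **1. The plan's own figure.** The plan states no precision for the smoking-rate model. Its quit-rate power reproduces. With 187 per arm (1:1 assumed) and 33% vs 47%, z = (0.14 − 1.96·√(2·0.40·0.60/187)) / √((0.33·0.67 + 0.47·0.53)/187) = (0.14 − 0.0993)/0.0501 = 0.81. Power is about 79%, against 80% stated.

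**2. True variance.** Let p be the share still smoking, with mean μ and variance μ + kμ² among them. Each arm's squared coefficient of variation is (1 + 1/μ + k)/p − 1. The true standard error (SE) of the log rate ratio is the square root of the sum over arms divided by n. The documents do not give μ or k. The assumed range is μ = 5–20/day and k = 0.1–1.0.

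Example at Week 24 with μ = 10, k = 0.3:
- Standard arm: 1.4/0.67 − 1 = 1.090. Extended arm: 1.4/0.53 − 1 = 1.642.
- True SE = √(2.731/187) = 0.121.

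**3. Model-based variance.** With dispersion a, the model uses 1/(μp) + a in each arm.
- Estimated dispersion averaged 2.47 in simulation at this setting: √((0.149 + 0.189 + 2·2.47)/187) = 0.168, which is 1.39 times the true SE.
- Fixed at 1: √((0.149 + 0.189 + 2)/187) = 0.112, which is 0.93 of the true SE.

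Simulated trials at 33% vs 47%, with no effect among continuing smokers, agree (arm-only model, 187 per arm, 800–1,500 runs, SE relative to empirical SD):

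| μ/day | k | Estimated | Fixed at 1 | Robust | Rejection, estimated vs robust |
|---|---|---|---|---|---|
| 10 | 0.1 | 1.47 | 1.03 | 0.96 | 0.23 vs 0.59 |
| 10 | 0.3 | 1.39 | 0.93 | 1.00 | 0.21 vs 0.49 |
| 10 | 0.6 | 1.32 | 0.84 | 1.05 | 0.19 vs 0.36 |
| 10 | 1.0 | 1.13 | 0.68 | 0.98 | 0.21 vs 0.31 |
| 20 | 0.1 | 1.85 | 1.11 | 1.04 | 0.11 vs 0.63 |
| 20 | 0.3 | 1.61 | 0.93 | 1.02 | 0.14 vs 0.52 |

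At μ = 5 the estimated-dispersion ratio is 1.03–1.27. For 7-day totals at 10/day with k = 0.1–0.6 it is 1.64–2.18.

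**4. False positives.** With no arm difference, over the same μ and k, estimated dispersion rejects mostly 0–4% of the time and dispersion fixed at 1 rejects 3–20%. The robust SE stays at 0.94–1.09 of the true value.

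**5. When a fixed dispersion of 1 is too small.** With equal p in both arms, compare (1 + 1/μ + k)/p − 1 with 1 + 1/(μp). The model variance is too small when k > 2p − 1.
- All randomised, p = 0.60: the threshold is k > 0.20, so either direction is possible.
- Only those with follow-up: confirmed abstainers must have attended, so zeros are about 0.40/0.70 = 57% and p = 0.43. The threshold is 2·0.43 − 1 = −0.14, so the SE is too small for every k.
- In the follow-up group (131 per arm) the simulated SE is about 0.55–0.86 of the true value, with false-positive rates of about 9–31%.

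**6. Quitting inside the ratio.** With no change among continuing smokers the ratio is (1 − 0.47)/(1 − 0.33) = 0.53/0.67 = 0.79 at Week 24 and 0.44/0.72 = 0.61 at Week 52. If extended-arm continuing smokers smoke 5%, 10%, 20% or 30% less, quitting makes up 82%, 69%, 51% or 40% of the Week 24 log ratio (for example, ln 0.79/(ln 0.79 + ln 0.80) = 51%). At Week 52 the shares are 91%, 82%, 69% and 58%.

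**The case against.** The strongest reply is that the documents give no distribution for cigarettes/day, so no single multiplier is a property of this plan. That stands. A reader might infer that the intervals are at least 1.4 times too wide, but the inputs do not support this. With a log-baseline covariate, 40% zeros, an assumed baseline mean of 5–13/day and continuing smokers at 65% of baseline, the model-to-robust SE ratio for daily counts was 1.00–1.48. Only one of 12 settings reached 1.4. Ratios near 2 come mainly from 7-day totals, whereas the plan's scale is cigarettes per day.

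Four other strong readings also fail:
- That fixing dispersion always makes intervals too narrow. In all randomised participants it can be about right or slightly wide.
- That at least a third of every arm will be zeros. The Week 52 standard-arm rate is 28%.
- That abstainers are certainly in the model. Intent-to-treat makes this the natural reading, but the text does not say so.
- That the ratio must be mostly quitting. This depends on an unknown effect among continuing smokers.

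It is also fair that the all-participant ratio is a legitimate randomised comparison, that the plan nowhere proposes to claim reduction among non-quitters, and that a smokers-only comparison conditions on a post-randomisation outcome. A reduction claim should therefore not be made to depend on that comparison. Smoking rate is a secondary outcome with no power statement, and with estimated dispersion the error is mostly conservative.

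The reply does not remove the mismatch between the named model and the expected data. Across nearly all of the assumed range the default SE is off in one direction or the other, while a robust SE is close to correct throughout.

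**Conclusion.** The point holds as a range. For daily counts, with continuing smokers averaging 5–20/day and dispersion 0.1–1.0, the model-based SE is about 1.0–1.9 times the true SE when dispersion is estimated, and more for 7-day totals. With dispersion fixed at 1 it runs from about right to about 0.65 of the true SE in all randomised participants, and is about 0.55–0.86 of it among those with follow-up data. These figures assume 1:1 allocation, one time-point, an arm-only model and abstainers included. The 0.79 and 0.61 ratios follow from the planned quit rates alone, and mean that the ratio must not be read as reduction among non-quitters. The change should be made, but the primary logistic analysis of abstinence does not depend on it.

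**What to change.** In Data Analysis, Aim 1:
- Name the response as the follow-up cigarette count at a stated time-point. Do not use a change score, which can be negative and cannot be fitted by a negative binomial.
- Analyse all randomised participants, abstainers included, with baseline rate as a covariate and a log link. State how a participant without a count is handled, since coding as a smoker supplies no number.
- Take the SE, confidence interval and p-value for treatment arm from a robust (sandwich) or bootstrap variance, and state how dispersion is set.
- Describe the ratio as the overall effect on consumption, including quitting. Cigarettes/day among continuing smokers may be reported beside it, labelled descriptive only.

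The cost is a few sentences of analysis-plan text and one software option, with no extra data.

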8. Complete baseline paper and pencil measures to assess 1) background variables that may serve as covariates and will allow for assessment of external validity (e.g., smoking history, demographics); 2) mediators (e.g., affect), 3) moderators (e.g., disease-related information), and 4) baseline smoking behavior.

If eligible at this point, subjects will be scheduled for the first treatment session (Week 0). There must be no more than 60 days between the Intake Session and the first treatment session (Week 0, Pre-Quit). If 60 days elapses between these sessions, all intake measures must be re-administered and evaluated by the study physician before Pre-Quit can occur (both sessions may be completed on the same day pending study physician approval by phone).

Behavioral Counseling (Week 0-Week 18).

All subjects will receive manual-based counseling from a counselor trained and supervised by [name]. The counseling protocol is based on PHS guidelines for smoking cessation treatment (Fiore et al., 2008), used in our past studies with cancer patients ([name] et al., 2010a) and in our ongoing cessation trial at NU (R01 DA025078). Counseling is included given its efficacy at helping smokers quit (Fiore et al., 2008) and to increase study retention. Counseling is provided to both treatment arms through Week 18 to equate for time and attention across arms and since this method was used in varenicline clinical trials (Gonzales et al., 2006) and in our extended therapy trial ([name] et al., 2010b). In-person counseling was selected for most sessions to ensure adequate monitoring of participant safety and adherence throughout the trial. Sessions are arranged at convenient times for the participants, including evenings.

Pre-Quit Session (Week 0): The counseling program begins at Week 0 with a 1-hour in-person "pre-quit" counseling session to prepare for the target quit day. This session focuses on reviewing participant's history and experience with quitting, beliefs about smoking and quitting, and perceived barriers to cessation, and

initiates a quitting plan involving identifying smoking triggers and identifying strategies to increase the chance for success, including relying on social support and altering behaviors associated with smoking. Medication is dispensed at this session and will begin following the session.

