We will also frequently assess participant treatment reactions with established varenicline symptom checklists and validated suicidality and depression scales. These assessments will be conducted at each visit before, during, and after the treatment phase. Also, given recent reports indicating the potential risk for adverse cardiovascular effects from varenicline (Singh et al., 2011 and www.fda.gov/Drugs/DrugSafety/ucm259161.htm), blood pressure will be assessed at each in-person visit to monitor cardiovascular reactions to study medication.

We will use an established coding and reporting system for side effects used in our ongoing multi-site varenicline trial (U01 DA020830). In this system, study personnel are trained by physicians and psychologists to administer established side effects measures, including validated scales of depression and suicidality. If a side effect report or a score on an established scale indicates a safety concern, site PIs and physicians/psychologists are immediately notified and will determine a course of action (e.g., continue to monitor, stop medication). Participants are given contact information so that, if an adverse event occurs, they can contact study physicians 24-hours a day. These side effects are also coded and managed by PIs and site physicians/psychologists. All serious adverse events are reported to the IRB, NIH, FDA, and Pfizer in accordance with data safety and monitoring reporting procedures, and they may also be referred to an out-patient department at PENN/NU or to the ER. Lastly, a study-specific Data Safety and Monitoring Board will be convened for this trial to monitor side effects.

Outcome Assessments.

The primary outcome variable is 7-day point prevalence abstinence at Weeks 24 and 52, confirmed with CO (Hughes et al., 2003). All participants will be asked to attend the center at Weeks 24 and 52 and CO will be collected for all participants to avoid potential bias. Other outcomes include: 7-day point-prevalence abstinence (CO-verified) at Week 12 and 26, smoking rate, prolonged abstinence to Weeks 12, 24, 26, and 52 (relapse defined as 7 consecutive days of self-reported smoking, after a 2-week grace period), continuous abstinence at Week 12, 24, 26, and 52 (no smoking between the quit day and the follow-up measure), time to 7-day relapse (no grace period), lapse and recovery events, and QOL.

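### The smoking-rate model does not say whether its response is a change score, which a negative binomial model cannot fit, or a follow-up count, for which no baseline smoking term is specified

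*Combined protocol and SAP*

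**What the plan says.** The model is given in one sentence under Data Analysis, Aim 1: the "negative binomial family log link for count data will be used to examine the main effects of treatment arm on changes in smoking rate". The reason offered is that "as many participants will fail to become completely abstinent".

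Other sections describe the outcome as follows:
- Outcome Assessments lists it among the outcomes other than the primary one, with no mention of change: "7-day point-prevalence abstinence (CO-verified) at Week 12 and 26, smoking rate, prolonged abstinence to Weeks 12, 24, 26, and 52".
- Outcomes Variables (Cessation/Smoking Rate) says: "Daily smoking (presence and rate) will be assessed at each visit after Intake Session". It adds that the data serve "as well as to monitor changes in smoking rates (i.e., # cigarettes/day").
- Baseline smoking is collected. The Intake Session measures include "3) moderators (e.g., disease-related information), and 4) baseline smoking behavior", and the same list says that smoking history may be used as a covariate. Demographic and Smoking History includes current rate in that history. Table 2 schedules the timeline follow-back (TLFB) from Week 0.
- The general covariate rule under Data Analysis brings in variables associated with treatment arm and with completing follow-up. The remark in Aim 1 that covariates may be included belongs to the logistic model. Nothing is said about covariates for the negative binomial model.
- No time-point, count window, offset or missing-count rule is given for this model.

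**The concern.** The stated response and the stated distribution do not fit together. A negative binomial variable takes the values 0, 1, 2 and so on, while a change in cigarettes per day is negative for anyone who improves. Everyone smokes at entry, since eligibility requires people "18 years of age or older who self-report smoking at least 5 cigarettes per week". A negative change is therefore the expected result of successful treatment.

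The analyst can make the model work by using the follow-up count as the response. Randomisation still makes that a fair comparison of arms, but it is no longer an analysis of change unless baseline enters as a covariate or offset. Entry has a low floor and no ceiling, so baseline consumption probably varies widely and is probably a strong predictor of later consumption. Leaving it out would cost precision.

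The choice of response, visit, window and adjustment is also left until the data are in hand, so several different analyses could be presented as the planned one.

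**Working it through.** **No stated figure to reproduce.** The plan gives no power, mean, SD or dispersion for smoking rate. Its only related figure is 80% power for the Week 24 quit rates. With 187 per arm (equal allocation assumed) and 33% vs 47%, a two-sided test at 0.05 has 79% power, which agrees.

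**Reading 1: the response is follow-up minus baseline.**
- The negative binomial log-probability at any negative value, for example −5, is minus infinity.
- Quitters alone: (33% + 47%) / 2 = 40% of participants have a negative value.
- Adding people who cut down needs assumptions. With baseline means of 10 to 20 cigarettes per day, reductions of 0 to 50% in non-quitters, a rate ratio of 0.85 in the extended arm and no missing data, 74% to 96% of changes are negative.
- Missing data lower that share if a missing count is set to baseline, because those changes are exactly zero. Accrual expects about 70% to complete follow-up, so at most about 70% can be negative. Simulation gave about 63% to 65%.
- Fitting a simulated change score failed: the GLM stopped on an undefined deviance and maximum likelihood returned no estimates. The same code fitted the follow-up count.

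**Reading 2: the response is the follow-up count.** The question is what a baseline term is worth.
- From the documents: N = 374, quit rates of 33% and 47%, and about 30% missing (100% − 70%).
- Assumed: lognormal baseline with median 13 per day; continuing smokers at about 70% of baseline; 10% fewer cigarettes in the extended arm; dispersion 4; quitters at zero; robust standard errors.

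| Baseline log-SD (assumed) | No missing: power without / with log baseline | Gain | 30% missing, set to baseline: without / with | Gain |
|---|---|---|---|---|
| 0.4 | 77% / 88% | 11 | 44% / 58% | 14 |
| 0.65 | 63% / 88% | 25 | 26% / 55% | 29 |
| 0.9 | 43% / 82% | 39 | 20% / 55% | 35 |

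Type I error was 4% to 5% in the null run without missing data. At 300 simulated trials the Monte Carlo standard error is √(0.5 × 0.5 / 300) ≈ 3 points, so differences of a few points mean nothing. A second set of runs with 30% missing gave 52% / 64%, 42% / 66% and 29% / 67%, which are gains of 12, 24 and 38 points. The gains agree better than the absolute levels do.

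A different scenario used a mean baseline of 15 per day, a 25% reduction in non-quitters, a rate ratio of 0.85, no missing data and model-based standard errors (300 trials). The standard error of the log rate ratio fell from 0.185 to 0.170 and power rose from 57% to 71%, a gain of 14 points.

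**The case against.** The strongest reply is that the wording is loose rather than wrong. The sentence itself says the model is for count data, smoking rate is defined as cigarettes per day, and the outcome lists say smoking rate without mentioning change. Where the plan means difference scores, as for the mediators in the Aim 3 power section, it says so. On that reading the model is an ordinary one. This stands, and it rules out three stronger conclusions that a reader might draw:

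- *That the analysis cannot be run as written.* This is true only of the change-score reading. The count reading is at least as natural.
- *That the plan omits baseline smoking.* No covariates are listed for this model, baseline rate is collected, and smoking history is named as a possible covariate. What the documents support is that baseline adjustment is not pre-specified. The general rule would add it only if it happened to be associated with arm and completion, because the rule does not select on prognosis.
- *That quitters would be dropped or recoded.* No section proposes this, and the plan commits to intent-to-treat. The stated motive about those who do not become abstinent might suggest an analysis of continuing smokers only, but the text does not say so.

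It is also fair to say that the power figures rest mainly on assumed inputs, and that the plan makes no power claim for this outcome.

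**Conclusion.** The point holds as a gap in specification. One reading of the sentence gives a model that cannot be fitted. The other gives a workable model with no stated baseline term, which does not address change and gives up precision.

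The 40% of negative values from quitting follows from the planned quit rates, given equal allocation. Any higher share depends on assumed reductions and on how missing counts are treated. The gain from adjustment, roughly 10 to 40 points of power, depends on the assumed baseline spread. Its direction was the same in every scenario tried. The absolute power levels should not be relied on: with adjustment they fell from 82–88% to about 55–67% once 30% missing follow-up was included.

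Smoking rate is a secondary outcome. The abstinence analyses, the sample size and data collection are unaffected. This should be corrected before analysis, but it does not threaten the trial's main conclusion.

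**What to change.** Reword the Aim 1 sentence so that it states:

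1. **Response:** total cigarettes recorded by TLFB over a stated window, for example 7 days, before Week 24 and before Week 52. A total over a window is an integer count, which a daily average need not be.
2. **Population:** all randomised participants, with quitters counted as zero.
3. **Model:** negative binomial with log link, with treatment arm and log baseline cigarettes per day from the Week 0 TLFB. Say how a zero Week 0 value would be handled, and whether standard errors are robust, given the excess zeros from quitters.
4. **Missing counts:** a rule consistent with coding missing participants as smoking. That convention gives a status and not a number of cigarettes, so a value is needed. The baseline count is one option. It is a debatable single imputation for about 30% of participants, including deaths, so a sensitivity analysis under a different assumption should be named with it.

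The cost is a wording change in the analysis section. The TLFB is already scheduled from Week 0 to Week 52, so no new data are needed.
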